#### 6.2.1.3 Assessment of Adverse Events

Each AE will be assessed by the Investigator with regard to the following categories.

##### 6.2.1.3.1 Seriousness

An SAE is defined as any untoward medical occurrence that at any dose:

- Results in death;
- Is life-threatening; This means that the subject is at risk of death at the time of the event; it does not mean that the event hypothetically might have caused death if it were more severe

**Note:** Whereas a systemic anaphylactic reaction is generally considered **potentially** life-threatening, not all anaphylaxis put the subjects at immediate risk of death, if for example appropriate treatments lead to symptoms reduction or disappearance. As per the Anaphylaxis Staging System (**APPENDIX 4**), an anaphylaxis assessed as mild or moderate should not be classified as life-threatening.

- Requires hospitalization (at least overnight stay or inpatient hospital admission) or prolongation of existing hospitalization;

Events associated with **hospitalization** for the following reasons will **not** be considered as an SAE:

1. Evaluation or treatment of a pre-existing (before informed consent signature) and non-exacerbating condition:
    - a. The condition existed prior to the subject's entry into the study and has been recorded in the subject's disease/medical history and the e-CRF *AND*
    - b. The condition has not worsened in severity or frequency during the subject's exposure to the IMP *AND*
    - c. The condition has not required a change in treatment management during the subject's exposure to the IMP;
  2. Hospitalization the day prior to or after the day of DBPCFC for practical reasons and without fulfilling any other seriousness criterion.
- Results in persistent or significant disability or incapacity (an AE is incapacitating or disabling if it results in a substantial and/or permanent disruption of the subject's ability to carry out normal life functions).;
  - Is a congenital anomaly or birth defect;
  - Is an important medical event that may not be immediately life-threatening or result in death or hospitalization but that may jeopardize the subject or require intervention to prevent one of the above outcomes. Examples of such events are intensive treatment in an emergency room or at home for allergic bronchospasm; blood dyscrasias or convulsions that do not result in hospitalization; or development of drug dependency or drug abuse.
    - An anaphylactic reaction classified as severe using the Anaphylaxis Staging System in **APPENDIX 4** (i.e., anaphylactic reaction with cyanosis or SpO2 ≤92%, hypotension with >20% drop in blood pressure, confusion, collapse, loss of consciousness) or requiring 3 or more epinephrine intakes should be reported at least with the seriousness criterion "important medical event";

- In the context of the DBPCFC, in addition to the severe anaphylaxis, the occurrence of:
  - Bronchospasm/audible wheezing with use of accessory muscles,
  - Severe angioedema
  - Admission in Intensive Care Unit and/or requirement of oxygen therapy
  - Intake of 3 or more doses of epinephrineshould be considered as meeting the seriousness criterion of “important medical event”

Medical and scientific judgment should be exercised in deciding whether a case is serious and whether expedited reporting is appropriate.

#### 6.2.1.3.2 Severity

The severity of each AE must be assessed by the Investigator using 1 of the following categories, and recorded in the e-CRF:

- Mild: The AE was transient and easily tolerated by the subject;
- Moderate: The AE caused discomfort and interference with the subject’s general condition;
- Severe: The AE caused considerable interference with the subject’s general condition and may have been incapacitating.

Anaphylaxis (including those reported as part of Medical History) will be graded in accordance to the Anaphylaxis Staging System (APPENDIX 4).

#### 6.2.1.3.3 Causality

The Investigator will assess the causality/relationship between the IMP and the AE and record that assessment in the source documents and in the e-CRF.

The most likely cause of an AE/SAE (for example disease under treatment, concomitant disease, concomitant medication, other) will be indicated in the e-CRF with details of the concomitant disease or medication or other cause.

The causal relationship of the AE to IMP will be described in terms of:

- Related: the AE:
  - Follows a clear temporal sequence from application of the IMP.
  - Has no other possible explanations, such as the subject’s clinical state, environmental or toxic factors or other therapies administered to the subject.
  - Disappears or decreases on cessation or reduction in dose of the IMP.
  - Follows a clear pattern of response to the IMP.
  - Reappears or worsens upon rechallenge.

- Probable: the AE:
  - Follows a reasonable temporal sequence from application of the IMP.
  - Could not be reasonably explained by the subject's clinical state, environmental or toxic factors or other therapies administered to the subject.
  - Disappears or decreases on cessation or reduction in dose of the IMP.
  - Follows a known pattern of response to the IMP.
  - Reappears or worsens upon rechallenge.
- Possible: the AE:
  - Follows a reasonable temporal sequence from application of the IMP.
  - Could be reasonably explained by the subject's clinical state, environmental or toxic factors or other therapies administered to the subject.
  - Follows a known pattern of response to the IMP.
- Unlikely: the AE
  - Does not follow a reasonable temporal sequence from application of the IMP.
  - Could be reasonably explained by the subject's clinical state, environmental or toxic factors or other therapies administered to the subject.
  - Does not follow a known pattern of response to the IMP.
  - Does not reappear or worsen upon rechallenge.
- Not related:
  - The AE does not meet the above criteria.
  - There is sufficient information that the etiology of the AE is not related to the IMP.

All SAEs assessed as related, probably related, and possibly related will be considered as related for expedited reporting (see Section 6.2.1.5).

The study conduct relatedness for SAEs will also be assessed and documented.

#### 6.2.1.3.4 Local Skin Reactions

The incidence, duration and maximum severity of skin reactions induced by the IMP will be reported by the subject's parents/guardians in the diary. Photos of these local reactions should be taken at home by the parents/guardians. Additionally, the Investigator or delegated trained staff, including but not limited to study nurses and physician assistants, will assess the severity of local skin reactions induced by the IMP at each site visit during the physical examination and photos should be taken during the site visits by the medical staff to document these local skin reactions (see Sections 6.2.4 and 6.2.6).

In addition, any occurrence of specific application site reaction will also be solicited at each study visit and phone contact among a pre-specified list of symptoms (see Section 6.2.1.1).

#### 6.2.1.3.5 Adverse Events of Special Interest

Adverse Events of Special Interest (AESI) to the Sponsor are defined as follows:

**Local AESI:** Any reaction at patch application site which could potentially lead to a skin barrier disruption, such as but not limited to, blister, vesicle, ulcerative skin lesion, bleeding or any Grade 4 patch site reaction.

Skin reactions will be examined at the time points specified in the Schedule of Procedures (page 15) according to grading in Table 3 (Section 6.2.6). Subject's parents/guardians will be instructed to take a photograph in case of appearance of any vesicles or ulcerative skin lesions. In these rare specific cases, subjects should transiently discontinue patch application and return to the site for evaluation and treatment of the wounded area, as well as for the next patch application and adequate evaluation and treatment of the wounded zone.

Upon re-application of the new patch, the subject should remain at the site for 1 hour before being discharged. The site must contact the subject's parents/guardians by phone the day after this visit to ensure that no additional local blisters or vesicles developed and to confirm that the treatment can continue normally. The zone with vesicles or severe lesions should not be used for patch application until it has completely healed.

**Local AESI should NOT be reported on the specific AESI form of the eCRF.** This specific AESI form is only to be used for systemic AESI (see below).

**Systemic AESI:** Any acute systemic immediate allergic reactions (rapid onset) after exposure to a known or suspected allergen regardless of the causal relationship to the IMP, and occurring outside the DBPCFCs:

1. Anaphylactic reaction:

- Any AE diagnosed by physician as an anaphylactic reaction, regardless of the severity and causal relationship to the IMP.
- Anaphylactic reaction defined as the occurrence of the following allergic symptoms:
  - Major acute allergic reaction (associated or not with other symptoms): acute hypotension (>20% drop in blood pressure) or associated cardiovascular symptoms (hypotonia, confusion, loss of consciousness, collapse, syncope, incontinence);
  - 2 or more concomitant acute allergic symptoms from at least 2 different organ systems such as, but not limited to:
    - Upper airway or respiratory symptoms (dyspnea, wheeze-bronchospasm, stridor, hypoxemia, decreased SaO2)
    - Acute and persistent gastro-intestinal symptoms (abdominal pain, cramps, vomiting)
    - Acute skin or mucosal tissue symptoms (angioedema, urticaria, pruritus, flush, swollen lips-tongue-uvula)
    - Acute cardiovascular symptoms (hypotonia, reduced blood pressure)

2. Any systemic hypersensitivity reaction leading to epinephrine intake

Any AE fulfilling the above definition must be ticked as an AESI in the AE form of the eCRF. In addition, these AESI must be documented and reported on a specific systemic AESI form by the Investigator on an ongoing basis (guidance and precisions will be given

in the eCRF Completion Guidelines). These specific systemic AESI forms must be completed and sent by the investigator within 24 hours of the site becoming aware of the event.

Potential anaphylactic reactions will be identified by dedicated Standardized MedDRA Queries (SMQ) algorithms. Cases retrieved by the algorithm will then be confirmed by medical review.

#### 6.2.1.3.6 Symptoms during to the Double-blind, Placebo-Controlled Food Challenge

The severity of the objective and subjective symptoms elicited during the entry and post-treatment DBPCFC will be assessed by the Investigator. These objective and subjective symptoms assessed by the Investigator will not be reported as single independent AE in the AE pages of the e-CRF. Complete information for all these symptoms will be reported in the DBPCFC pages of the e-CRF, along with all peanut protein doses given, the symptoms observed, the time of appearance of the symptoms and their specific grades, the time of grade change of each symptom, the doses of epinephrine given, the doses of corticosteroids and antihistamines given and the Investigator's assessment of the peanut ED as well as the peanut cumulative dose. If, as per the Investigator's judgment, the combination of all these symptoms resulted in an anaphylaxis requiring a prolonged (minimally overnight) hospitalization, then this will be considered an SAE. Any such SAE with its specific verbatim (e.g. 'during food challenge' or 'due to food challenge') must be reported in the AE pages of the e-CRF.

#### 6.2.1.4 Recording Adverse Events

Adverse event reporting will start at the signature of the informed consent form (ICF) and end after the 2-week follow-up period (Visit 12: End of Study Visit).

During the screening period (that is, from the time of ICF signature through Day-1), only SAEs will be recorded in the e-CRF; and AEs that do not meet any seriousness criteria will only be documented in the subject's source documents.

Adverse events occurring after the end of the study should be reported to the Sponsor by the Investigator if the Investigator considers that there is a causal relationship with the IMP.

Adverse events still ongoing at the time of the End of Study Visit will be followed up for an additional 30 days, or until they resolve or stabilize, whichever comes first.

All AEs occurring on or after the day of the first dose of IMP, regardless of the relationship to the IMP, will be recorded in the e-CRF.

All AE reports in the e-CRF should contain the following information of the event: date and time of onset, date and time of resolution, severity, treatment required, relationship to IMP, action taken with the IMP, outcome, and whether the event is classified as serious or not.

#### 6.2.1.5 Reporting Serious Adverse Events and AESI of allergic systemic reaction

- All SAEs must be reported within 24 hours of the site becoming aware of the event by filling in the SAE pages in the e-CRF. In case of technical issues with the e-CRF, the reporting can be done by sending a completed SAE Report Form to the DBV Global Safety and Pharmacovigilance team at the email address indicated on

the SAE Report : CCI This mailbox is monitored for any incoming SAE report.

The minimum information required for an initial report is:

- Name of person sending the report (that is name and address of Investigator);
- Subject identification (screening number, NOT the subject's name);
- Protocol number;
- Description of the SAE including a comprehensive verbatim term;
- Causality assessment.

However, as far as possible all points in the SAE pages in the e-CRF (or on the SAE Report Form, in case of technical issues with the e-CRF) should be covered in the initial report. If an SAE occurs during the DBPCFC, the verbatim of the SAE must specify "during the DBPCFC" or "due to the DBPCFC" both on the SAE Report Form and in the SAE pages of the e-CRF.

- Treatment emergent systemic AESIs defined in the e-CRF Completion Guidelines provided to the Investigator and regardless of their causal relationship to the IMP must also be reported within 24 hours of the site becoming aware of the event, by filling the systemic AESI specific report form in the e-CRF. In case a systemic allergic reaction is associated with a seriousness criteria, an SAE report form must be completed instead.

Sponsor will either directly or through contracted service providers submit expedited and periodic reports to both Competent Authorities and Ethics Committees as per regulations and procedures in force, taking into account local specific requirements.

SAEs that are both related (according to the sponsor and/or the investigator) to investigational medicinal product and unexpected (according to sponsor and based on the investigational product Reference Safety Information in use) will usually be assessed as reportable by the Sponsor to Competent Authorities.

#### **Waiver to expedited reporting:**

In case an anaphylactic reaction is experienced during the DBPCFC and assessed as serious by the investigator, this event should be reported within 24 hours of awareness by the investigational site as for other SAEs. Allergic reactions are voluntarily triggered by an "allergen" protein matrix (placebo matrix or "allergen" protein matrix) during the DBPCFC procedures and anaphylaxis are elicited events. These anaphylactic reactions will be considered as expected, if not leading to death (See [APPENDIX 9](#) for Reference Safety Information related to DBPCFC peanut protein matrix). Serious anaphylactic reactions assessed as related to the DBPCFC will not be subject to expedited reporting, unless they lead to death.

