#### ***4.3.2 Study Stopping Rules***

The safety of DBV712 is continuously monitored by the DBV medical monitor and the independent DSMB. However, the study will be suspended pending an expedited safety review by the independent DSMB if any of the following occur:

1. Any death related to DBV712 patch dosing;
2. More than 3 cases of severe anaphylaxis (stage 3 anaphylaxis, see [APPENDIX 4](#)) related to DBV712 patch application (not occurring during the DBPCFC);
3. More than 5 subjects requiring more than 2 injections of intramuscular epinephrine for an AE related to the DBV712 patch application, and not occurring during the DBPCFC nor related to an accidental food allergen consumption.

Upon safety review, the DSMB will recommend 1 of the following outcomes:

- The study may continue without modification;
- The study may continue with modifications as prescribed by the DSMB;
- The study should be discontinued.

The study will be prematurely stopped if the Sponsor, Regulatory Authorities, or Independent Ethics Committees (IECs)/Institutional Review Boards (IRBs) for any reason, request to stop the study.

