#### *6.1.1.1 Preparation of Peanut protein and Placebo Formulas*

Standardized formulas, centrally produced by CCI [REDACTED], and packed and released by CCI [REDACTED], will be distributed to all participating centers for the DBPCFC. One of the formulas will be peanut protein-free (placebo) and the other one will contain peanut proteins. An unblinded person identified at each site by the investigator, specifically trained to reconstitute the formulas in the study and not involved in the challenge itself will be responsible for the preparation, adequate labeling and blinding of the pots containing the prepared/hydrated formulas. The blinded pots will then be handed to the medical team to perform the challenge.

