#### 6.1.1.3 Entry/screening DBPCFC

Subjects who have not had an IgE-mediated reaction leading to stopping the DBPCFC at  $\leq 300$  mg peanut protein will be considered not sensitive enough and thus ineligible for this study. Hence, the entry/screening DBPCFC is stopped after the 300 mg dose of placebo or peanut has been dispensed on both days; even if there have been no reactions meeting the challenge stopping criteria.

Subjects will receive one formula (placebo or peanut) on the first day and the other formula (peanut or placebo) on the second day. All subjects will undergo both days of the DBPCFC.

If the subject reacted severely or seriously during the first day of the challenge (i.e. need for intubation, hypotension persisting after epinephrine administration, and/or the need for  $\geq 3$  doses of epinephrine), the nature of the administered formula will be highly suspected to be the peanut-containing formula. In this rare case and only in this case only, the second day of the DBPCFC cannot be performed. The blind on the formula will be opened at the end of the first day to confirm that the subject actually received the peanut formula.

At the end of the second day of challenge, the sequence of the two formulas will be unblinded and revealed to the medical staff by the unblinded person responsible for reconstituting the formulas and the results of the challenge will be established following the decision-making algorithm below:

1. The subject had IgE-mediated symptoms meeting the challenge stopping criteria to the placebo formula at any dose of the challenge. She/he cannot be randomized in the study;
2. The subject had no IgE-mediated symptoms meeting the challenge stopping criteria during the 2 days of the DBPCFC, neither to the placebo nor to the peanut formulas, even at the 300 mg dose of peanut protein. She/he cannot be randomized in the study;
3. The subject had no symptom meeting the challenge stopping criteria when receiving placebo but had symptoms meeting these criteria at one of the doses of the peanut formula consumed between 1 mg and 300 mg inclusive.

The following should be considered to stop the challenge and to determine the ED:

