### 5.5.1.3 Analyses

AEs related to accidental peanut consumption will be excluded from analyses (unless otherwise specified) and presented separately (section 5.7.1).

SAEs elicited during DBPCFC will be excluded from any analyses, unless otherwise specified. Nevertheless, these SAEs will be presented in the listings when applicable (section 5.6). Symptoms related to DBPCFC are reported in tables separately from other AEs.

For each summary presented by SOC and PT:

- the SOC “General disorders and administration site conditions” will be tabulated globally as well as split in 2 subsections:
  - General disorders (High Level Term not equal to “Application and instillation site reactions”),
  - Administration site conditions (High Level Term equal to “Application and instillation site reactions”).
- Lowest Level Term (LLT) will be tabulated for the PT “Anaphylactic reaction” to help distinguish reactions due to other allergens.

An overall overview table of TEAEs (to be distinguished from symptoms/reactions elicited during the DBPCFCs) will be provided showing the number of subjects, the percentage of subjects and the number of events for the following categories of TEAEs:

- Any TEAEs,
- Any serious TEAEs,
- Any TEAEs considered related to IMP:
  - Any TEAEs reported as related,
  - Any TEAEs reported as probably related,
  - Any TEAEs reported as possibly related,
- Any TEAEs considered unrelated to IMP:
  - Any TEAEs reported as unlikely related,
  - Any TEAEs reported as unrelated,
- Any Serious TEAEs considered related to IMP,
- Any TEAEs leading to permanent study treatment discontinuation,
- Any TEAEs leading to temporary study treatment discontinuation,
- Any TEAEs leading to death,
- Any mild TEAEs,

CONFIDENTIEL / Ne pas diffuser sans autorisation de DBV

CONFIDENTIAL / Do not distribute without DBV authorization

	Statistical Analysis Plan	
	EPITOPE (V712-304) – Statistical Analysis Plan	
	Référence du Document /Document Reference : CCI	Page : 52 / 74

CCI

- Any moderate TEAEs,
- Any severe TEAEs,
- Any severe TEAEs considered related to IMP (reported as related, probably or possibly related),
- Any IMP-induced Local TEAEs,
- Any severe IMP-induced Local TEAEs,
- Any treatment-emergent local AESI,
- Any treatment-emergent systemic AESI:
  - Reported as Anaphylactic reaction
  - Reported as Systemic hypersensitivity reaction leading to epinephrine intake

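### The expedited-reporting waiver classes non-fatal serious anaphylaxis after the peanut-free placebo formula as expected, so a case judged challenge-related triggers no expedited report from the sponsor

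*Protocol*

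**What the plan says.** Protocol section 6.2.1.5, under the waiver heading, makes four statements about anaphylaxis in the challenge.

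- The site reports a serious case within 24 hours, like any other SAE.
- The reactions are described as deliberately provoked. The parenthesis naming what provokes them covers both formulas: "protein matrix (placebo matrix or" the allergen one.
- On expectedness: "These anaphylactic reactions will be considered as expected, if not leading to death". The reference safety information cited (Appendix 9) is described as relating to the peanut protein matrix.
- On onward reporting: "Serious anaphylactic reactions assessed as related to the DBPCFC will not be subject to expedited reporting, unless they lead to death".

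None of these separates a peanut-formula day from a placebo-formula day. Section 6.1.1.1 does separate them: "One of the formulas will be peanut protein-free (placebo) and the other one will contain peanut proteins". The same section says that the formulas are produced centrally, sent to all centers, and then reconstituted, labelled and blinded by one unblinded person at each site.

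**The concern.** A reaction is expected in a challenge because the child is fed the allergen on purpose. That reasoning does not carry over to a formula without the allergen. If a child has a serious anaphylaxis on the placebo day, the likely explanations are a fault or an unknown. The formula may have been contaminated in central production, the pots may have been swapped or mislabelled at the site, or the child may have an allergy to a matrix component that nobody knew of. An investigator could reasonably assess each of these as related to the challenge, and that assessment is what brings the event under the waiver.

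At stake is the speed with which authorities and ethics committees learn of a possible defect in a product fed to every challenged child at 50 to 70 planned sites. The efficacy analysis is not affected.

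**Working it through.** No power or error-rate figure is involved. The check sets the passages side by side and then sizes the exposure.

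**1. How the protocol treats a placebo-formula reaction elsewhere**

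| Place | Treatment |
|---|---|
| 6.1.1.1 | Placebo formula contains no peanut protein |
| 4.2, exclusion 3 | A stopping-criteria reaction to it at screening excludes the child |
| 4.2, exclusion 8 | Known hypersensitivity to a formula component excludes the child |
| 6.1.1.3, algorithm item 1 | IgE-mediated stopping symptoms on placebo at any dose: not randomized |
| 6.2.1.5, waiver | Provoked on purpose, expected unless fatal, no expedited report |

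The first four rows treat the reaction as an anomaly. Only the waiver treats it as the intended result.

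**2. When the formula is known**

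The sequence is normally opened at the end of the second challenge day, and section 6.1.1.2 allows up to 7 days between the two days. Earlier opening applies after intubation, persistent hypotension after epinephrine, or three or more epinephrine doses: "The blind on the formula will be opened at the end of the first day". Section 6.1.1.4 applies the same procedures at Month 12. Seriousness in section 6.2.1.3.1 is wider and includes overnight hospitalization, severe angioedema and oxygen therapy. A serious case on day 1 can therefore stay blinded for up to 7 days. The visible text does not require expectedness to be reassessed when the sequence is opened, and it does not say what follows for reporting if an early opening shows placebo.

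**3. Whether another route covers the event**

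- Systemic AESI (6.2.1.3.5): defined as occurring outside the challenges.
- Study stopping rule (4.3.2): counts severe anaphylaxis "related to DBV712 patch application (not occurring during the DBPCFC". It addresses a different hazard and would not count a formula reaction whatever the waiver said.
- SAP 5.5.1.3: "SAEs elicited during DBPCFC will be excluded from any analyses, unless otherwise specified". The events remain in listings, and SAP 5.6.1 tabulates them by formula, but those outputs follow database lock.
- DSMB (9.11): may review safety data at intervals and ad hoc, but no rule sends it this event.

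**4. Exposure**

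Inputs: about 400 randomized, up to 60% screen failure, 350 in Part B, and at most 15% drop-out (sample-size text in the synopsis and section 8.10).

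- Children screened: 400 / (1 − 0.60) = 1,000, which reproduces the protocol's figure.
- Screening placebo days: at least about 400, because a child must complete the entry challenge to be randomized, and at most about 1,000, because some fail before Visit 2.
- Month 12 placebo days in Part B: 350 × (1 − 0.15) ≈ 298, up to 350.
- Total: 400 + 298 ≈ 700, up to 1,000 + 350 = 1,350. Part A would add up to 50 at Month 12.

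The documents give no rate of serious anaphylaxis on placebo days, so no expected count can be derived.

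**The case against.** The strongest case on the other side is that most of the safety net is intact. A reader might infer that these events would not be reported promptly at all. The waiver itself contradicts that: the site must inform the sponsor within 24 hours. SAEs are entered in the e-CRF with wording that marks them as arising in the challenge, the medical monitor and DSMB monitor safety continuously, and periodic reports continue. All of this stands. What is lost is only the sponsor's onward expedited report.

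A reader might also infer that a patch reaction could hide under the waiver. The documents do not support that as a general claim. The waiver covers only events assessed as related to the challenge. An SAE judged related to the IMP and unexpected remains reportable under the ordinary rule in section 6.2.1.5. At screening no patch has yet been applied (first application is at Visit 4). At Month 12 the patch is removed before the challenge, so a patch reaction would escape only by being attributed to the challenge.

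A third objection has more force. The specific authority-reporting rule in section 6.2.1.5 concerns SAEs related to the IMP. A contaminated formula is not the IMP, so removing the waiver might not by itself produce a report. But the waiver keeps fatal challenge-related anaphylaxis under expedited reporting. The protocol therefore treats challenge-related events as otherwise in scope, and the waiver does remove something. The objection shapes the fix: sending the event back to the ordinary SAE route is not enough.

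Finally, the content of Appendix 9 is not visible. It may say something about the placebo matrix. The protocol describes it only as relating to the peanut protein matrix.

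**Conclusion.** The point holds in a limited form. The waiver misclassifies non-fatal serious anaphylaxis after the peanut-free formula as provoked and expected. If such a case is judged related to the challenge, no expedited report goes to authorities and ethics committees, even when contamination, mislabelling or an unrecognised matrix allergy is a possible cause. This is a stated rule in conflict with sections 4.2, 6.1.1.1 and 6.1.1.3, not a missing detail.

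The number of cases is presumably very small over roughly 700 to 1,350 placebo days. The weight comes from the fact that one case could point to a fault in a formula shared by all sites. The conclusion rests on two assumptions: that Appendix 9 matches its description in the text, and that such a case would be assessed as challenge-related. It is worth correcting, but it does not show that the safety reporting fails as a whole.

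**What to change.** In the waiver paragraph of section 6.2.1.5:

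1. Strike the mention of the placebo matrix from the parenthesis.
2. Limit both the expected status and the waiver to serious anaphylaxis after the confirmed peanut formula.
3. State outright that serious anaphylaxis after the placebo formula is not expected and is outside the waiver, whether or not it is judged related to the IMP.
4. Require expectedness and causality to be reassessed as soon as the sequence is opened: at the end of day 1 where the blind is opened early, otherwise at the end of day 2. State how a serious day-1 case is handled while its formula is still blinded, which can be up to 7 days.

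The reference safety information in Appendix 9 and the safety plan should be aligned with this. The cost is one or two sentences and possibly a few extra expedited reports. No treatment, challenge procedure or analysis changes.
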